16.1.6 Presentation of PK Concentration and PK Parameter Data

16.1.6.1 Listings and Tables

The following PK tables will be produced (PK Analysis Set):

- Descriptive statistics of concentrations by analyte and study intervention
- Descriptive statistics of PK parameters by analyte and study intervention

The following PK Listings will be produced (Safety Analysis Set):

- Individual concentrations, nominal time by participant, analyte, and study intervention sorted in chronological order
- Individual PK parameters by participant, analyte, and day sorted in chronological order
- PK Sampling date, actual time, nominal time, deviation from time, percentage time deviation by participant, analyte, and study intervention sorted in chronological order
- Phoenix WinNonlin NCA Core Output

16.1.6.2 Graphical Summaries and Individual plots (PK Analysis Set)

The following graphical summaries and individual plots will be provided:

- Overlaid individual plasma concentration versus time plots on linear and semi-log scale, using actual times, by analyte, and study intervention
- Individual plasma concentration versus time plots overlaid for each study intervention by participant and analyte on linear and semi-log scale using actual times. If any postdose concentration is BLQ the line representing LLOQ will be added to the semi-log plots
- Arithmetic mean concentration time plots; linear (\pm SD for arithmetic mean) and semi-log; using scheduled (nominal) time points by analyte, and study intervention; if any postdose concentration is BLQ the line representing LLOQ will be added to the semi-log plots
- Median concentration time plots; linear and semi-log; using scheduled (nominal) time points by analyte, and study intervention; if any postdose concentration is BLQ the line representing LLOQ will be added to the semi-log plots
- Boxplots for PK parameters $AUC_{0-\infty}$ and C_{max} by analyte, and study intervention

16.2 Pharmacodynamics

Not applicable.

16.3

QTc Analysis

For QTc analysis, the ECG analysis set will be used.

As a first step, ECG assay sensitivity will be demonstrated via C-QTc analysis of data following administration of moxifloxacin as described in Section 16.3.4.

Subsequently, the relationship between observed evobrutinib CCI plasma concentrations and time-matched, triplicate QTc intervals will be evaluated in a C-QTc analysis as described below in Section 16.3.3. The correction of the observed QT intervals will be based on the Fridericia correction (QTcF). If adequate correction of the observed QT data for heart rate is not obtained with the Fridericia correction and there is a meaningful effect of evobrutinib and MSC2729909A on HR (i.e. greater than 10 bpm as described in Section 16.3.3.1), individual-optimized RR correction methods (QTcI) may be applied in a supplemental analysis.

CCI

Primary and secondary endpoints will be summarized by timepoint as described in Section 16.3.4.3.

16.3.1

Data Selection for C-QTc Analysis

For the C-QTc analysis, PK samples and ECG measurements will be matched by nominal time point, unless the ECG and PK sample times are more than 15 minutes apart, in which case the ECG record will be flagged for exclusion from the analysis.

Parameters to be considered in the C-QTc analysis include QTcF intervals, uncorrected QT intervals, and heart rate (HR). In addition, QTcI may be considered based on correction factors derived from predose and placebo data.

A NONMEM-formatted analysis dataset will be constructed based on data from ECG analysis set. The dataset will include information on participant ID, period identifier, nominal and actual date and time of PK sample collections, evobrutinib plasma concentrations, MSC2729909A plasma concentrations, and time-matched ECG measurements, as well as relevant covariates (age, body weight, sex, and race). As a general principle, missing concentration and ECG data will not be imputed. Concentration values below the limit of quantification will be treated as 0. The exact format of the dataset will be described and agreed upon through a data specification document.

Assembly of the C-QTc dataset will be performed using SAS® Software version 9.2 or higher. C-QTc analysis will be performed using NONMEM 7.3 or higher or R version 4.1 or higher. Model diagnostics, evaluation, and model predictions will be performed using R version 4.1 or higher. Actual software versions will be reported. Quality control (QC) of the dataset programming will be performed per Certara standard operating procedures.

16.3.2

C-QTc Analysis Dataset Summary and CCI

Absolute and baseline-corrected ECG measurements and evobrutinib, MSC2729909A, and moxifloxacin plasma concentrations will be summarized by period/time point, a summary of participants and observations in the analysis dataset will be provided, and a listing of participants and data records flagged for exclusion from the C-QTc analysis will be created.

The mean observed evobrutinib, MSC2729909A, and moxifloxacin plasma concentrations and absolute and baseline-corrected ECG measurements will be shown vs nominal time point for each treatment group (placebo, moxifloxacin, 45 mg evobrutinib, 225 mg evobrutinib), and baseline-corrected ECG measurements will be shown vs time-matched PK data. In addition, plots of QT, QTcF, and QTcI vs RR will be created to illustrate the heart rate correction of the available QT data.

16.3.3

Primary Objective Analysis: C-QTc analysis

The relationship between evobrutinib, MSC2729909A, and moxifloxacin plasma concentration and QT intervals will be carried out based on heart rate-corrected QT data (QTc). QTc should be independent of HR or RR interval ($HR=60/RR$) in the evaluation of drug-induced QT prolongation. Fridericia-correction shown in **Equation 1** is considered the gold standard, however, the adequacy of the Fridericia correction will be assessed by a linear regression of QTcF interval on the RR interval.

$$QT_{cF} = \frac{QT}{RR^{1/3}} \quad \text{Equation 1}$$

CCI

A linear mixed effects modeling approach will be used to quantify the relationship between evobrutinib (and metabolite) and moxifloxacin plasma concentration and $\Delta QTcF$, provided that QTcF is independent of RR interval and no evidence of drug-induced heart rate changes, no hysteresis, and no clear indication of nonlinearity in the concentration- $\Delta QTcF$ relationship is identified [1, 2]. Data-driven C-QTc models will be developed when one or more of the assumptions discussed in Section 16.3.3.1 are violated.

The standard linear mixed-effects model is described in Section 16.3.3.2. A covariate analysis will be performed to refine the developed structural model by including covariates that have a statistically significantly effect on QTc as described in Section 16.3.3.3.

16.3.3.1 Evaluation of Assumptions

Assessment of Drug Effect on HR

The potential of evobrutinib and MSC2729909A to increase or decrease heart rate by more than 10 bpm will be assessed graphically by plotting the mean observed Δ HR with 90% confidence interval versus timepoint for each treatment group and visually inspecting the trend of consistence with time and treatment group and, if applicable, based on model predicted Δ HR with 90% confidence versus corresponding evobrutinib and/or MSC2729909A plasma concentrations (see Section 16.3.4.2). Treatment groups with a small number of participants may be grouped together for this purpose. The Δ HR-concentration relationship may be further evaluated by scatter plots of individual time-matched Δ HR vs concentration pairs.

Hysteresis

To assess visually whether there is a time lag (a hysteresis effect) between evobrutinib plasma concentration and Δ QTc interval, mean concentration and mean Δ QTc will be plotted versus timepoint for each treatment group in a single plot and visually inspected for differences between t_{max} for concentration and t_{max} for Δ QTc. In addition, individual and mean plots showing Δ QTc and concentration connected in the order of ECG measurements/PK sampling will be shown for each study participant and evobrutinib treatment group, respectively. If the relationship between Δ QTc and evobrutinib plasma concentration appears independent of time, this suggests no hysteresis. If the exploration shows that the value of Δ QTc for a given value of concentration differs as time evolves, and the values of Δ QTc observed before t_{max} consistently differ from the values observed at a similar concentration at a timepoint after t_{max} , this suggests presence of hysteresis [1,3].

CCI

Assessment of Linearity

[figure not shown]
The relationship between observed ΔQTc and evobrutinib and MSC2729909A plasma concentrations will be visualized by decile plots showing mean observed ΔQTc with 90% confidence intervals placed at the midpoint of each concentration decile, as well as scatter plots of ΔQTc versus concentration for all timepoints from all treatment groups. Locally estimated scatterplot smoothing (LOESS) curve and linear regression lines will be included in the scatter plots.

CCI

[figure not shown]
[figure not shown]
[figure not shown]
[figure not shown]
[figure not shown]

16.3.3.2 Standard Linear Mixed-Effects Model of QTc

[figure not shown]
The recommended linear mixed effects model described by Garnett et al. [1] will be applied in the C-QTc analysis to quantify the relationship between evobrutinib and CCI

CCI

CCI

Similar methodology will be applied in the C-QTc analysis of ECG measurements following administration of moxifloxacin or placebo in the evaluation of assay sensitivity, as described in Section 16.3.4.

16.3.3.3 Covariate Analysis

Covariates of interest for the C-QTc models are (apart from nominal time) age, body weight, sex, race, and study period. Covariates will only be evaluated as predictors of parameters with random effects.

For a covariate to be included in the formal covariate analysis, it should be available in at least 80% of participants. For categorical covariates, if a category constitutes less than 10% of the total participants, it will be combined with the most prevalent category. Multiple low proportion categories may be grouped together as a single category.

Covariate analysis will only be performed if a statistically significant C-QTc relationship is found ($P<0.01$). A multivariable forward addition of significant covariates ($P<0.01$) followed by backward elimination of not significant covariates ($P>0.001$) will be performed on univariable significant covariates ($P<0.01$). Only one of a highly correlated pair of univariable significant covariates will be included in the multivariable analysis. The model emerging from the multivariable covariate evaluation may be refined to ensure model identifiability and plausibility of included covariate relations.

In the covariate evaluation, the maximum likelihood (ML) estimation option will be selected instead of the restricted maximum likelihood (REML) option. A REML criterion is inappropriate to compare models differing in fixed effects while ML is consistent with the likelihood-ratio test used in the covariate evaluation. Final run results will use the "REML" option; results will be compared with "ML" results to confirm minimal differences.

16.3.3.4 Model Selection and Evaluation

The standard model shown in Equation 5 will be considered the primary model of $\Delta QTcF$. If the assessment of QT interval correction indicates that the Fridericia-correction is not adequate (see Section 16.3.3), the standard model may be fitted to $\Delta QTcI$ in an additional supplemental analysis. If indicated by model diagnostics, additional models may be evaluated, and a data-driven model may be presented.

For nested models, a log-likelihood criterion at the 0.01 level of significance will be used for model selection; for non-nested models, the Akaike Information Criterion will be used. The final model will be selected based on the statistical comparisons described above, diagnostic plots, and clinical plausibility and relevance. A model building summary and parameter estimates (with 95% confidence intervals (CIs) and relative standard errors) for the standard and (if applicable) empirical models will be provided.

Diagnostic plots will include plots of observed vs. model-predicted ΔQTc , observed and model-predicted ΔQTc intervals versus time, quantile-quantile plots of standardized residuals, and plots of standardized residuals vs. predicted ΔQTc , concentration, time after dose within period, and treatment (placebo, 45 mg evobrutinib, 225 mg evobrutinib). Distributions of random effects will be shown in histograms and quantile-quantile plots, and correlations between random effects will be shown in a pairwise scatterplot. Correlations between random effects and covariates will be shown in scatter plots with LOESS (continuous covariates) or box-whisker plots (categorical covariates). The predicted concentration- ΔQTc relationship will be overlaid on corresponding observed data on a continuous concentration scale and summarized by concentration bins (e.g. deciles). The 90% CI of the observed mean ΔQTc will be based on a normality assumption.

The predictive performance of the developed final C- ΔQTc model will be evaluated using visual predictive checks (VPC). The distribution of observed data will be compared to corresponding simulated data to demonstrate the model's ability to adequately predict the data on which the model is based. VPC will show data vs time after first dose and vs concentration. VPCs will be based on 1000 simulations.

The model diagnostics and evaluation will be based on the overall dataset and stratified by subject covariates included in the final model. If the final model includes both evobrutinib and MSC2729909A, two alternative individual models based on only evobrutinib and only MSC2729909A will be estimated and used for figures representing the underlying data (scatter plots for C-QTc model, decile plots, and prediction plots).

For data-driven, non-linear C-QTc models, a non-parametric bootstrap with subject identifier used as the unit for resampling may be carried out to confirm model robustness, as well as for computing confidence intervals on model predictions (see Section 16.3.3.5).

16.3.3.5 Model-Based Predictions

The predicted placebo- and baseline-corrected QTc will be denoted $\Delta\Delta QTc$ and calculated as the difference between the model-predicted ΔQTc at relevant evobrutinib and MSC2729909A plasma concentrations and ΔQTc predicted for participants treated with placebo [1]. CCI [REDACTED]

[REDACTED]

[REDACTED]

[REDACTED]

CCI

Predictions based on additional and/or data-driven models (if relevant, see Section 16.3.3.4) will be calculated based on corresponding model equations.

CCI

16.3.4 Secondary Objective Analysis

16.3.4.1 QTc Assay Sensitivity

The evaluation of assay sensitivity based on the data from the positive control will be based on estimates and model predictions based on the standard linear mixed-effects model of QTcF fit to data obtained following administration of moxifloxacin (see Section 16.3.3.2). Predictions of $\Delta\Delta QTc$ following moxifloxacin exposure will follow the methodology described in Section 16.3.3.5. The evaluation of assay sensitivity will be based on the assumption that the assumptions described in Section 16.3.3.1 (no evidence of drug-induced heart rate changes, adequate correction of QTcF for heart rate, no hysteresis, and no clear indication of a nonlinear relationship between concentration and ΔQTc) are met.

CCI

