4.2 Scientific Rationale for Study Design

The design of this thorough QT study, a randomized, assessor-blinded, placebo- and positive-(moxifloxacin) controlled, single-dose, 4-period crossover study, is the standard design for this type of QT assessment study.

4.2.1

Use of Moxifloxacin

A positive control is recommended by regulatory authorities to be able to detect a ~ 5 ms change from baseline- and placebo-corrected QTc duration ($\Delta\Delta\text{QTc}$) to confirm the sensitivity of the study. Moxifloxacin is frequently used in thorough QT studies because it induces small and consistent prolongations of QT/QTc but is not considered as having a proarrhythmic activity (as outlined in ICH E14/S7B Q&A 2020). A pooled analysis of 14 crossover thorough QT studies with 400 mg single oral dose of moxifloxacin demonstrated a largest mean $\Delta\Delta\text{QTcF}$ effect of 12.3 ms at 3 h postdose (Yan 2010). In this study, a single 400 mg dose of moxifloxacin will be administered orally to the participants (refer to approved product information).

4.2.2

Participant Input into Design

Not applicable.

4.3

Justification for Dose

Evobrutinib

The evobrutinib therapeutic dose to be used in this study [REDACTED] CCI is expected to result in C_{max} similar to those in the Phase 3 studies in patients dosed with 45 mg tablets (fed) BID, and the supratherapeutic dose [REDACTED] CCI is expected to result in 5-fold higher C_{max} . A [REDACTED] CCI higher C_{max} is expected to provide adequate coverage for the clinically relevant high-exposure scenario for evobrutinib C_{max} , if administered with a moderate or strong CYP3A4 inhibitor [REDACTED] CCI

Moxifloxacin

Moxifloxacin is frequently used in thorough QT studies because it induces a small and consistent QT/QTc prolongation with a low incidence of inducing proarrhythmic activity. A single oral dose of 400 mg given in a fasted state is the standard dose used for this type of study.

4.4

End of Study Definition

The end of the study is defined as the date of last contact (related to this study) with the last participant who participates in this study (last participant's Safety Follow-up Assessment/Early Termination Assessment).

A participant has completed the study if he/she has completed all study parts including the Safety Follow-up Assessment shown in Section 1.3.

Study Termination Criteria

The study will be discontinued or terminated if:

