9.4.2 Other Analyses (QTc and PK analyses)

Reference #	Endpoint	Statistical Analysis Methods
Primary		
1	$\Delta\Delta QTcF$ (evobrutinib)	A mixed-effects model with repeated measures will be used to analyze the relationship between evobrutinib concentrations and $\Delta\Delta QTcF$. Based on this model, the predicted $\Delta\Delta QTcF$ at clinically relevant concentrations will be calculated, with two-sided 90% confidence intervals. Model selection, including consideration of linear and nonlinear function to describe the C-QTc relationship, will be based on graphical exploration, along with standard goodness-of-fit plots. Additionally, the effects of evobrutinib on $\Delta\Delta QTcF$ will be descriptively summarized at each postdose timepoint (by timepoint analysis). Number and frequency of QTcF values within specified ranges will be summarized. Further details will be described in the IAP.
Secondary		
2	$\Delta\Delta QTcF$ (moxifloxacin)	Assay sensitivity will be demonstrated by showing that the lower bound of the 90% CI of the predicted $\Delta\Delta QTcF$ (from C-QTc model) for moxifloxacin at the observed geometric mean C_{max} at 400 mg dose exceeds 5 ms. Further details will be described in the IAP.
4	$\Delta\Delta HR$, $\Delta\Delta PR$, $\Delta\Delta RR$, $\Delta\Delta QRS$, T-wave morphology and U-wave	The effects of evobrutinib on these endpoints will be evaluated at each postdose timepoint (by timepoint analysis). Further details will be described in the IAP.
5	PK parameters (in Section 8.4)	Summary statistics of PK parameters will be provided. All PK analyses will be performed on the PKAS.

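### Does taking the linear-model assumptions as met for moxifloxacin put the assay-sensitivity test at risk?

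*SAP*

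**What the plan says.** SAP 16.3 puts the positive control first: "As a first step, ECG assay sensitivity will be demonstrated via C-QTc analysis". Protocol 9.4.2 gives the criterion. The lower bound of the 90% CI for the model-predicted ΔΔQTcF "for moxifloxacin at the observed geometric mean" Cmax must exceed 5 ms.

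Two SAP sections deal with the model for moxifloxacin:

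- SAP 16.3.3 names moxifloxacin beside evobrutinib and its metabolite. It allows the linear model "provided that QTcF is independent of RR interval and no evidence of drug-induced heart rate changes, no hysteresis, and no clear indication of nonlinearity". It then adds: "Data-driven C-QTc models will be developed when one or more of the assumptions discussed in Section 16.3.3.1 are violated".
- SAP 16.3.4.1 specifies the standard linear model for moxifloxacin and states: "The evaluation of assay sensitivity will be based on the assumption that the assumptions described in Section 16.3.3.1" are met, listing the same four conditions.

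Some of the diagnostics are described for evobrutinib only. In SAP 16.3.3.1 the plots that join concentration and ΔQTc in time order "will be shown for each study participant and evobrutinib treatment group, respectively", and the decile and scatter plots for linearity name evobrutinib and its metabolite. In SAP 16.3.3.4 standardized residuals are plotted against "time after dose within period, and treatment (placebo, 45 mg evobrutinib, 225 mg evobrutinib"; moxifloxacin is not on that list.

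**The concern.** One section attaches a condition and a consequence to the linear model; the other appears to presuppose the condition. Suppose moxifloxacin showed a clear delay between concentration and effect. An analyst following SAP 16.3.3 would move to another model, while one following SAP 16.3.4.1 literally would keep the line. That choice would be made after the data had been seen, at the step that decides whether a negative evobrutinib result can be interpreted.

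The direction of the error is also plausible. A straight line fitted to a delayed response is flattened, so its value at Cmax lies below the true peak effect. A study able to detect a 5 ms effect might then fail its positive control.

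**Working it through.** **Side-by-side reading.** Four places bear on moxifloxacin besides the two sections in apparent conflict.

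1. SAP 16.3.3.2 says similar methodology is used for the moxifloxacin and placebo data in the assay-sensitivity evaluation.
2. SAP 16.3.4.1 sends its predictions to SAP 16.3.3.5, which says how predictions are formed from additional or data-driven models.
3. The first hysteresis check in SAP 16.3.3.1 overlays mean concentration and mean ΔQTc against time for each treatment group. SAP 16.3.2 lists moxifloxacin among those groups. It also plots baseline-corrected ECG values against time-matched concentrations.
4. SAP 16.3.4.3 tabulates, for each active treatment, the largest by-timepoint mean ΔΔQTcF with its 90% CI. That gives a model-free view of moxifloxacin.

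So a moxifloxacin delay would be visible, and a route for handling it is written down. Redacted blocks also stand in SAP 16.3.3.1 and directly after the sentence in 16.3.4.1; they cannot be counted as gaps.

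**How large could the bias be?** No sample size, SD or power for the positive control is readable, so there is no plan figure to reproduce.

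Inputs from the documents:

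- peak effect "effect of 12.3 ms at 3 h postdose" (Protocol 4.2.1)
- Cmax 3.1 mg/L, reached at 0.5 to 4 h (Protocol 2.2)
- 13 postdose sampling times from 0.25 to 24 h (Protocol 1.3)
- threshold 5 ms, 90% CI (Protocol 9.4.2)

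Assumed inputs:

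- one-compartment absorption, ka 0.6 to 6 per h
- elimination half-life 9 to 15 h
- effect-delay half-life h up to 2 h

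Formulas:

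- C(t) ∝ exp(−ke·t) − exp(−ka·t), scaled to a maximum of 3.1 mg/L
- dCe/dt = (ln 2 / h)·(C − Ce)
- E(t) = 12.3 · Ce(t) / max Ce
- Fit E = a + b·C by least squares at the 13 times; prediction P = a + b·Cmax

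| Delay half-life h | P (true peak 12.3 ms) |
|---|---|
| about 0 | 12.2 to 12.3 ms |
| 0.25 h | 11.2 to 12.1 ms |
| 0.5 h | 10.5 to 11.6 ms |
| 1 h | 8.9 to 10.6 ms |
| 2 h | 6.8 to 9.3 ms |

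Keeping only scenarios whose effect peaks near the protocol's 3 h (2.75 to 3.25 h), P is 9.8 to 12.3 ms. The shortfall is at most 12.3 − 9.8 = 2.5 ms, against a gap of 12.3 − 5 = 7.3 ms.

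**Effect on passing.** With standard error SE, P(pass) = Φ((P − 5)/SE − 1.645).

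| P | SE 1.5 ms | SE 2 ms |
|---|---|---|
| 12.3 ms | Φ(3.22) = 0.999 | Φ(2.01) = 0.98 |
| 11.0 ms | Φ(2.36) = 0.99 | Φ(1.36) = 0.91 |
| 9.8 ms | Φ(1.56) = 0.94 | Φ(0.76) = 0.78 |

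A simulation of moxifloxacin/placebo crossovers (2000 per cell) assumed typical t_max 1.5 h, residual SD 6 ms per triplicate mean and between-period SD 4 ms. The prediction's SD was about 1.5, 1.25 and 1.05 ms for N = 24, 32 and 48. Pass rates:

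| True peak | Delay half-life | N = 24 | N = 32 | N = 48 |
|---|---|---|---|---|
| 12.3 ms | none | 100% | 100% | 100% |
| 12.3 ms | 0.5 h | 99% | 100% | 100% |
| 12.3 ms | 1 h | 96% | 99% | 100% |
| 10 ms (assumed) | none | 95% | 99% | 100% |
| 10 ms (assumed) | 0.5 h | 87% | 93% | 98% |
| 10 ms (assumed) | 1 h | 72% | 79% | 90% |
| 8 ms (assumed) | none | 68% | 79% | 88% |
| 8 ms (assumed) | 0.5 h | 46% | 55% | 69% |

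With t_max 1 to 2 h and a 12 h elimination half-life, a 0.5 h delay puts the peak effect at 2.7 to 3.3 h, close to the documented 3 h. A 1 h delay puts it at 4.2 to 4.6 h, later than documented.

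**The case for a change.** The strongest case for a change is that the two sections differ on their face, that the positive control gates the interpretation, and that one sentence would align them at almost no cost. If the true peak were 10 ms instead of 12.3 ms, a 0.5 h delay would cost 8 percentage points at N = 24 (95% to 87%), and a 1 h delay would cost 23 (95% to 72%).

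The wording point stands: 16.3.4.1 is loosely drafted. The rest carries less weight. No document supports an 8 or 10 ms peak, and at 8 ms with N = 24 the study would fail 32% of the time with no delay at all. Nor do the documents show a delay: a 3 h peak effect lies inside the stated 0.5 to 4 h window for peak concentration.

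A delay model would not be a clear improvement either. Under a delay, concentration alone does not determine the effect, so a prediction at geometric mean Cmax has no single meaning. With ka 3 per h, half-life 12 h and h = 0.5 h, the effect at the moment of Cmax is 9.9 ms, the linear prediction is 11.0 ms and the peak is 12.3 ms. The line is too low against one target and too high against another. Choosing the model after seeing the data would also give the positive control a second route to passing. Extra tests at 2, 3 and 4 h, held as supportive evidence, would not alter the decision.

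**Conclusion.** The concern does not call for a change. The sentence in SAP 16.3.4.1 can be read as restating the condition in 16.3.3, and the cross-references to 16.3.3.2 and 16.3.3.5, with the by-treatment plots, give analysts enough to check moxifloxacin and handle a clear violation sensibly. Keeping a fixed linear model for the positive control is also a fair trade-off: it is simple, set in advance and, if a delay exists, conservative relative to the peak effect.

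At the documented 12.3 ms near 3 h, the shortfall is 0 to 2.5 ms, and the simulated pass rate is 99 to 100% for a 0.5 h delay. The exposure is larger only with a large standard error (78% at the extreme 9.8 ms prediction with SE 2 ms) or a true effect well below 12.3 ms. These figures rest on assumed pharmacokinetics, delays, SDs and sample sizes, because the plan's own values are not readable. The direction of the error does not depend on the sample size or SDs: a delayed effect could cost the sponsor a valid negative result, but would not make an insensitive study look sensitive.
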